6 STUDY OBJECTIVES

6.1 Primary Objective

[figure not shown]
The primary objective of this study is to demonstrate noninferiority of the Clareon/Clareon Toric IOLs to the Eyhance/Eyhance Toric IOLs in binocular BCDVA at 3-months postoperative.

[figure not shown]
Table 6-1 Primary Objective

[figure not shown]
Objective	Endpoint
To demonstrate noninferiority of the Clareon/Clareon Toric IOLs to the Eyhance/Eyhance Toric IOLs in binocular BCDVA at 3 months postoperative.	Mean binocular BCDVA under bright lighting conditions at 4 m at 3 months postoperative visit.

6.2 Secondary Objective

Not applicable. There are no secondary objectives in this study.

6.5 Safety Objectives

There are no safety objectives. However, safety endpoints will be collected and summarized.

Table 6-3 Safety Objectives

Objectives	Endpoints
None	
• All adverse events (ocular and non-ocular, serious and non-serious)• SSI• Device deficiencies• IOL observations• IOL position change (tilt and decentration) from slit lamp examination

Objectives	Endpoints
	
• PCO• Posterior capsulotomy• Surgical problems• Other surgical procedures• Slit lamp examination• Dilated fundus examination• IOP

7 INVESTIGATIONAL PLAN

7.1 Study Design

This is a prospective, multi-center, randomized, double masked (subject and VA assessor), parallel group, postmarket study.

The study will enroll approximately 185 subjects who will be randomized to bilateral implantation of either Clareon/Clareon Toric IOLs or Eyhance/Eyhance Toric IOLs. The study will include adults 22 years of age and older, diagnosed with cataracts in both eyes, and planned bilateral cataract removal by routine small incision phacoemulsification surgery.

Eligible subjects should have planned implantation of a toric IOL, either test or comparator IOL per randomization from the following model numbers: CNW0T3, CNW0T4, CNW0T5, CNW0T6 or DIU150, DIU225, DIU300, DIU375 with approximately 1.00 - 3.00 D of preoperative corneal astigmatism in at least one eye at the Preoperative Visit (Visit 0). **It is preferred that both eyes have preoperative astigmatism between 1.00 – 3.00 D.** It is recommended that the eye with the highest astigmatism be implanted first. If the astigmatism is the same in both eyes, it is at the surgeon's discretion to determine which eye is implanted first.

Changes in lens selection (diopter power and/or toricity) are permitted intraoperatively if recommended by the Optiwave Refractive Analysis (ORA) or similar equipment. However, the lens selected intraoperatively must meet the same preoperative requirements of:

- 1) target emmetropia or first minus for the predicted residual refraction*,
- 2) have a predicted residual cylinder of ≤ 0.50 D, and

[figure not shown]
3) be within the diopter range (10.0 – 25.0 D) and toric model up to a maximum of CNW0T6 or DIU375 depending on the randomization group.

*Surgeons may change the planned IOL power and resulting predicted residual refraction for the 2nd eye based on the first eye outcomes so long as the predicted residual refraction within +/- 0.50 D. This should only be used to adjust in the case of a refractive surprise and should NOT be used to implant patients with mini-monovision. If ORA (or similar equipment) recommends that the patient subject receive a non-toric IOL (Clareon SY60WF or Eyhance DIB00), then the subject may receive this non-toric IOL implantation and continue in the study.

It is recommended that Visit 00 (1st eye surgery) occur within 0 to 30 calendar days after the Preoperative Visit (Visit 0). It is allowable for the 2nd eye to be operated on the same day as the 1st eye per the investigator's medical judgement. It is recommended that the 2nd eye surgery occur no longer than 14 days after the 1st eye surgery. **Note:** If a subject must re-schedule 1st eye surgery (Visit 00) and the date exceeds 60 days from Visit 0, the subject may continue study participation if Visit 0 biometry, tonometry, slit lamp examination, and dilated fundus exam assessments are repeated and occur within 60 days of the rescheduled surgery, and the subject is confirmed to continue to meet all entry criteria.

A total of up to 7 scheduled visits are planned: the Screening/Visit 0 and two Operative Visits (Visit 00 and Visit 00A), Visit 1, Visit 1A, Visit 2A and Visit 3A. Postoperative visits must occur at the following intervals: Visit 1/1A (Days 1-2) after 1st and 2nd eye surgery respectively, Visit 2A (Days 30-60) after the 2nd eye surgery, and Visit 3A (Days 90-120) after the 2nd eye surgery.

Figure 7-1 Study Diagram

* Option for the 2nd eye to be operated on the same day as the 1st eye. It is recommended that Visit 00 (1st eye surgery) occur within 0 to 30 calendar days after the Preoperative Visit (Visit 0). If not occurring on the same day, the 2nd eye IOL implantation should be conducted within 14 days after 1st eye implantation.

7.2 Rationale for Study Design

This prospective, multi-center, randomized, double masked (subject and VA assessor), parallel group, postmarket study aims to compare two partial-corneal correcting aspheric monofocal IOLs with different aspheric profiles. The head-to-head design, randomization and double masking provide the most robust method of comparison between the IOLs while reducing potential bias. The IOLs were identified for their potential similarity using pre-clinical testing and clinical literature reviews which have led to the noninferiority statistical plan. Both IOLs will be applied on label and as described within the package insert.

7.4 Rationale for Duration of Treatment/Follow-Up

The duration of subject follow-up for this study will allow for the short-term assessment (3 month) of the IOLs included in this study.

Both the Clareon/Clareon Toric IOLs and the Eyhance/Eyhance Toric IOLs are currently marketed products.

7.5 Rationale for Choice of Comparator Product

The study lenses are both partial-corneal correcting aspheric monofocal IOLs with different aspheric profiles. The Clareon/Toric IOL has a uniform aspheric surface, and Eyhance/Eyhance Toric IOLs has a graduated aspheric surface. [REDACTED]

[REDACTED]. The IOLs were identified for their similarity using pre-clinical testing and clinical literature reviews.

7.6 Data Monitoring Committee

Not applicable

8 STUDY POPULATION

The study population consists of adults 22 years of age or older, diagnosed with binocular cataract who require bilateral cataract extraction by phacoemulsification.

We aim to enroll (consent) approximately 185 subjects in approximately 10 sites in the US with a target of approximately 23-31 subjects per site. Each site should contribute no more than 25% of the total enrolled study sample size. Site-specific targets may vary based upon individual site capabilities. The estimated time needed to recruit subjects for the study is approximately 5 months, however, unanticipated circumstances may shorten or lengthen this time and would not require amendment of this protocol.

Assuming a 10% screening failure rate and 16% dropout rate, data from approximately 140 subjects (70 subjects per group) will be available for statistical analysis at 3 months.

Enrollment projections are as follows:

- Approximately 185 subjects to be enrolled (sign consent) (a 10% screen failure rate is estimated)
- Approximately 168 subjects randomized (approximately 84 per group) to be bilaterally implanted (a 16% dropout rate is estimated)

- Minimum 140 subjects (approximately 70 subjects per group) to successfully complete the final study visit (Visit 3A)

Check all entry criteria at Screening/Visit 0 and at both surgical visits (Visit 00, Visit 00A). If a subject is excluded following enrollment and prior to 1st eye surgery (IOL does not come in contact with the eye), the subject should be discontinued from participation in the study.

Refer to Section 8.4 Reasons for Discontinuation (During Surgery) for further details.

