Subject population	
Adults 22 years of age or older, diagnosed with bilateral cataracts, who require bilateral cataract extraction by phacoemulsification
 
Planned number of enrolled/consented subjects: Approximately 185 subjects (approximately 93 subjects per group)
 
Planned number of randomized subjects: Approximately 168 subjects (approximately 84 subjects per group)
 
Planned number of completed subjects: Approximately 140 subjects (approximately 70 subjects per group)

Sites and Locations	
Planned number of clinical sites: ~10 sites
 
Planned locations: US

Key inclusion criteria (See Section 8.1 for a complete list of inclusion criteria)	
 • Adults (at least 22 years of age or older at the time of screening) diagnosed with cataract in both eyes. • Planned bilateral cataract removal by routine small incision phacoemulsification surgery

	
• Planned implantation of either test or comparator IOL (per randomization) from the following model numbers: CNW0T3, CNW0T4, CNW0T5, CNW0T6 or DIU150, DIU225, DIU300, DIU375 in at least one eye with approximately 1.00 – 3.00 D of preoperative corneal astigmatism• Predicted postoperative astigmatism of ≤ 0.5 D in both operative eyes based on a Toric calculator• Pupil restriction with a penlight to ≤ 3.5 mm

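### Does a target of 23-31 subjects per site at about 10 sites contradict the planned total of 185 in a way that calls for a change?

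*Protocol*

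**What the plan says.** Protocol section 8 (Study Population) puts the three recruitment figures in one sentence: "approximately 185 subjects in approximately 10 sites in the US with a target of approximately 23-31 subjects per site". The Protocol Summary (section 3) repeats the site count: "Planned number of clinical sites: ~10 sites". Section 8 then adds two qualifiers. One is a cap: "Each site should contribute no more than 25% of the total enrolled study sample size". The other is a flexibility clause: "Site-specific targets may vary based upon individual site capabilities".

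The total of about 185 consented subjects also appears in the Protocol Summary, in protocol section 7.1 and in SAP section 1.2. Section 8 goes on from 185 consented, with 10% screen failure, to about 168 randomised (84 per group), and then, with 16% dropout, to 140 completers (70 per group). The completer figure is called approximate in one sentence of section 8 and in the Protocol Summary, and a minimum in the section 8 list of projections.

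**The concern.** A reader who multiplies sites by subjects per site does not get 185, or anything close to it. All ten sites cannot work to 23-31 subjects each while the trial stops at 185. The written average of 18.5 is below the bottom of the target range.

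Three consequences might be feared:

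- Sites that recruit to their written target could take the trial 45-125 subjects past its planned total.
- Investigators obtain both lens types themselves and must have them ready on the surgery day, so a wrong target could mislead their ordering.
- Randomisation is blocked by site (SAP section 1.3), so sites stopped short of target might complete fewer blocks and be less well balanced between arms.

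The attrition chain also looks slightly short if it is run forward from 185, because it ends just under the stated minimum of 140, and protocol section 10.4.2 does not allow replacement.

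**Working it through.** **Inputs.** From protocol section 8: total consented 185, sites 10 (also in section 3), target 23-31 per site, cap 25%, screen failure 10%, dropout 16%, randomised 168, completers 140.

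**1. Sites times per-site target, against 185**

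| Sites | x 23 | x 31 | Excess over 185 | 185 / sites |
|---|---|---|---|---|
| 6 | 138 | 186 | -25.4% to +0.5% | 30.8 |
| 8 | 184 | 248 | -0.5% to +34.1% | 23.1 |
| 9 | 207 | 279 | +11.9% to +50.8% | 20.6 |
| 10 | 230 | 310 | +24.3% to +67.6% | 18.5 |

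At 10 sites the stated total is not reproduced. The excess is 230 - 185 = 45 to 310 - 185 = 125 subjects. Solving for the number of sites gives 185/31 = 5.97 and 185/23 = 8.04. The range therefore equals 185 spread over 6 to 8 sites almost exactly at both ends. If the target is read as randomised subjects, the gap widens: 168/10 = 16.8 per site.

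**2. The cap**

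0.25 x 185 = 46.25, so 46 subjects. Both 18.5 and 31 are below 46, so the cap conflicts with neither figure.

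**3. The attrition chain**

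- Back from completers: 140 / 0.84 = 166.7, so 167, against 168 stated.
- Forward from randomised: 168 x 0.84 = 141.1, against 140 stated.
- Back from randomised: 168 / 0.90 = 186.7, so 187, against 185 stated. A simple 10% uplift gives 168 x 1.10 = 184.8, which matches 185 and is probably how the figure was obtained.
- Forward from consented: 185 x 0.90 = 166.5, then x 0.84 = 139.9, against 140 stated.

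The differences are two subjects or fewer, on figures given as approximate and on assumed rates. The planned totals agree with each other.

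**4. Where the per-site figure could enter the analysis**

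- Primary test (protocol section 12.4.3, SAP section 4.3.1): difference in means by two-sample t-test, with Levene's test deciding between equal and unequal variances. There is no site term.
- Success rule: the upper one-sided 95% confidence limit must not exceed 0.1 logMAR. No site quantity appears in it.
- Study conduct summaries (SAP section 3.1): subjects randomised and lens models by investigator. These are descriptive counts of what happened.
- Randomisation (protocol section 9.3, SAP section 1.3): 1:1, blocked by site. Neither section ties the list to a site's recruitment target.

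In the text that is public, no calculation uses 23-31.

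**The case for a change.** The strongest case for a change is that the word approximately cannot absorb a gap of 24-68%, and that the flexibility clause does not help. It lets single sites differ, but it cannot bring the average of ten sites into a range whose lower end is 23 while the total stays at 185. For example, if five sites enrol 23 each (115 subjects), the other five share 70, or 14 each. Investigators plan from this sentence, and correcting it would cost only a few words.

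The arithmetic in that case stands. The sentence is internally inconsistent, and neither redaction nor PDF extraction explains it. The stated harms do not stand:

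- **Over-enrolment.** It would require every site to reach its target and the sponsor to disregard its own total, which the protocol and SAP state consistently. Nothing in the documents makes the total the sum of the site targets.
- **Procurement.** Lenses are bought locally through ordinary commercial channels (protocol section 9.5.1), and unused product may go back to the investigator's general stock (section 9.5.5). A mistaken expectation of volume is absorbed there.
- **Balance.** With blocking, a site that closes leaves at most its last block incomplete, whether it averaged 18.5 or 23 subjects. The block size is not given, but this holds for any size. The primary t-test does not condition on site, so an incomplete block does not affect its validity.
- **Attrition.** The forward result of 139.9 arises only by replacing the protocol's own 168 with 166.5, and it rounds to 140 anyway. Raising 185 to 187 would mean editing the total in protocol sections 3, 7.1 and 8 and in SAP section 1.2, along with the 93 per group in the Protocol Summary, for no real difference.

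**Conclusion.** The concern is right on the arithmetic but gives no reason to change the plan. The per-site range is 24-68% too high for ten sites and is best read as a clerical leftover from a plan with 6-8 sites. That origin is an inference from how closely both ends fit.

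The range is a loose recruitment guide beside a total that is stated consistently. The hypothesis, margin, test, analysis set and planned 70 completers per group do not depend on it, and the 185/168/140 chain agrees within about two subjects. Correcting the range would not alter the results or the conclusion.

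This rests on two assumptions. First, the sponsor closes enrolment at about 185 across all sites, as the protocol and SAP both say, and does not let each site run to its own target. Second, the redacted text, including the sample size justification, makes no use of the per-site figure. That is very likely, because the sample is planned per group and the visible primary test has no site component.

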8.1 Inclusion Criteria

Subjects eligible for inclusion in this study must fulfill **all** of the following criteria:

1.	Adults 22 years of age and older (at the time of screening) diagnosed with cataracts in both eyes.
2.	Able to comprehend and willing to sign an IRB/IEC approved informed consent.
3.	Planned bilateral cataract removal by routine small incision phacoemulsification surgery.
4.	Planned implantation of either test or comparator IOL (per randomization) from the following model numbers: CNW0T3, CNW0T4, CNW0T5, CNW0T6 or DIU150, DIU225, DIU300, DIU375 in at least one eye with approximately 1.00 – 3.00 D of preoperative corneal astigmatism.
5.	Predicted postoperative astigmatism of $\leq 0.5D$ in both operative eyes based on a Toric calculator.
6.	Calculated IOL power between 10.0 D and 25.0 D when targeted for emmetropia or first minus residual refraction.
7.	Potential postoperative best corrected distance visual acuity of 0.2 logMAR or better in both eyes based on the Investigator’s expert medical opinion (Note: Subjects with any pathology that could reduce visual potential should not be enrolled in this study).
8.	Pupil constriction with a penlight to ≤ 3.5 mm.
9.	Pupil able to dilate to > 6.0 mm.

10.	Clear intraocular media other than cataract.
11.	Willing and able to complete all required postoperative visits.

8.2 Exclusion Criteria

1.	Any disease or pathology, other than cataract, that (in the Investigator’s opinion) may reduce the potential BCDVA to a level worse than 0.2 logMAR (including, but not limited to the following: clinically severe corneal dystrophy (e.g., epithelial, stromal, or endothelial dystrophy), diabetic retinopathy, extremely shallow anterior chamber, not due to swollen cataract, microphthalmos, previous retinal detachment, previous corneal transplant, recurrent severe anterior or posterior segment inflammation of unknown etiology, iris neovascularization, glaucoma, aniridia, or optic nerve atrophy, epiretinal membrane, or diagnosis of pseudoexfoliation).
2.	History of or concurrent macular degeneration.
3.	Clinically significant (in the Investigator’s opinion) corneal pathology (epithelial, stromal, endothelial), dry-eye or ocular surface disease that would adversely affect a) the biometry measures and/or toric calculations and b) the visual outcome. This includes, but is not limited to old significant corneal scars (including Salzmann’s nodular degeneration), corneal irregularity (including dry eye syndrome), active or inactive keratitis with compromise of the refractive capability of the cornea, keratoconjunctivitis sicca with compromise of visual function, active keratouveitis, endothelial dystrophy (Fuch’s and non-guttate), keratoconus, etc.
4.	Clinically significant ocular trauma or ocular surface disease that would affect study measurements based on the Investigator’s expert medical opinion.
5.	History of previous intraocular or corneal surgery (including iridotomy and laser-assisted in situ keratomileusis (LASIK)).
6.	Women of childbearing potential, defined as all women who are physiologically capable of becoming pregnant and who are not postmenopausal for at least 1

	
year or are less than 6 weeks since sterilization, are excluded from participation if any of the following apply:
 
a. They are currently pregnantb. Have a positive urine pregnancy test result at Screeningc. Intend to become pregnant during the study periodd. Are breast-feeding 
Subjects who become pregnant and/or lactating after a study lens has been implanted in (or contacted) their eye will not be discontinued; however, data will be excluded from the effectiveness analyses because pregnancy and/or lactating can alter refraction and visual acuity results.

7.	History of amblyopia or monofixation syndrome with poor stereoscopic vision.
8.	Any use (current or historical) of an alpha-1-selective adrenoceptor blocking agent or an antagonist of alpha1A adrenoceptor (e.g., Flomax (tamsulosin HCL), Hytrin (terazosin), Cardura (doxazosin), or Uroxatral (alfuzosin)).
9.	Any subject currently participating in another investigational drug or device study that may confound the results of this investigation.
10.	Any other ocular or systemic co-morbidity that, in the Investigator's opinion, may confound the results of this study or prohibit the completion of the study assessments or increase the risk for the subject.
11.	Subjects with conditions that, in the Investigator's opinion, increase the risk of zonular rupture during cataract extraction procedure (e.g., Marfan syndrome) that may affect the postoperative centration or tilt of the lens.
12.	Any other planned ocular surgical procedures including but not limited to limbal relaxing incision (LRI), astigmatic keratotomy, LASIK, and retinal laser treatment within the study time frame.
13.	Patients who desire monovision/mini-monovision.

14.	Presumed or actual ocular infection (bacterial, viral, fungal) or history of ocular herpes (simplex or zoster) in either eye as determined by subject history and/or examination at Visit 0 per the investigator’s expert medical opinion.
-----	--

8.3 Rescreening of Subjects

Rescreening of subjects is not allowed in this study.

8.4 Reasons for Discontinuation (During Surgery)

Below are listed reasons to not implant the study lens.

1.	Surgical complications including but not limited to loss of zonular integrity/zonular weakness, zonular rupture, anterior or posterior capsule rupture interfering with the stability of the IOL, any evidence of fluid misdirection during the cataract procedure with progressive shallowing of the anterior chamber, uncontrollable IOP.
2.	Mechanical or surgical manipulation of the pupil.
3.	Excessive iris mobility.
4.	Inability to place the IOL in the capsular bag due to surgical complications.

Subjects may be excluded from trial participation during surgery. For specific criteria, refer to protocol Section 8.4 Reasons for Discontinuation During Surgery. Depending on the circumstance, the subject may continue in the study or may be discontinued as outlined in [Table 8-1](#) below. In addition, the subject may be excluded from trial participation if lens implantation was unsuccessfully attempted more than twice. Table 8-1 below applies in these circumstances as well. A subject discontinuing at the time of surgery will not be considered as a screen failure.

Table 8-1 Subject Status after Exclusion During Surgery

Conditions	Status/Follow-up

 • Exclusion during surgery occurs • IOL did not touch eye 	
 • Subject discontinued

Conditions	Status/Follow-up

 Exclusion during surgery occurs IOL did touch eye Lens is not implanted 	
 Subject continued No effectiveness assessments conducted at postoperative visits Safety assessments conducted at postoperative visits

 Exclusion during surgery occurs Lens implanted 	
 Subject continued Effectiveness assessments conducted at postoperative visits Safety assessments conducted at postoperative visits

Note: Unilateral IOL implantation is NOT allowed in this study; thus, if the subject’s 1st eye is not implanted with study IOL, the subject should be discontinued from the study.

In the event the 2nd eye is not implanted with study IOL (following a successful implant with a study IOL in the 1st eye), the subject will remain in the study and complete all required testing except for binocular VA assessments and subject questionnaires. Surgeon questionnaires should still be completed for the study eye.

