10.4.2 Discontinuations

Discontinued subjects are individuals who voluntarily withdraw or are withdrawn from the study by the Investigator after informed consent is signed, are randomized to treatment and before the last study visit is completed.

Subject numbers of discontinued subjects must not be re-used (i.e., subject replacement is not allowed). Subjects may discontinue from the study or study treatment at any time for any reason. Subjects may also be discontinued from study treatment at any time if, in the opinion of the Investigator, continued treatment poses a risk to their health.

The Investigator must document the reason for study or treatment discontinuation in the subject's case history source documents. To ensure the safety of all subjects who discontinue early, Investigators must assess each subject and, if necessary, advise them of any therapies and/or medical procedures that may be needed to maintain their health.

10.4.3 Schedule of Procedures and Assessments for Subjects Discontinued from Investigational Product

Subjects who discontinue the IP (i.e., have study lens explanted) will continue in the study through Visit 3A and be followed for safety. At minimum, safety examinations must include the assessments associated with appropriate medical care. Standard post-surgical assessments are bulleted below:

- UCDVA and/or BCDVA
- Slit-lamp Examination
- Dilated Fundus Examination

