12.2 Analysis Sets

The primary analysis set for effectiveness will be the All-Implanted Analysis Set (AAS). The AAS will include all eyes with successful study IOL implantation and with at least one postoperative visit.

All eyes with attempted study IOL implantation (successful or aborted after contact with the eye) will be considered evaluable for the safety analysis set (SAS).

The primary analysis set for effectiveness will be the AAS, [REDACTED]
[REDACTED]
[REDACTED]
[REDACTED]

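### Protocol 8.4 both continues and discontinues a subject whose first eye was touched by the study lens but not implanted

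*Protocol*

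**What the plan says.** Protocol Section 8.4 sets a subject's status after exclusion during surgery in two places.

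Table 8-1 sorts by lens contact and implantation and names no eye:

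- Row 1, lens did not touch the eye: "Subject discontinued".
- Row 2, lens touched the eye but was not implanted: the subject continues, with safety assessments at postoperative visits and "No effectiveness assessments conducted at postoperative visits".
- Row 3, lens implanted: the subject continues with both kinds of assessment.

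The note below the table sorts by eye and ignores contact. It opens by ruling out unilateral implantation and concludes that if the "1st eye is not implanted with study IOL, the subject should be discontinued from the study". The next paragraph covers a second eye left without a study lens after a successful first eye: "the subject will remain in the study and complete all required testing except for binocular VA assessments and subject questionnaires".

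Protocol Section 7.1 schedules the later visits from the second operation only: "Visit 2A (Days 30-60) after the 2nd eye surgery, and Visit 3A (Days 90-120) after the 2nd eye surgery". The safety analysis set (Protocol 12.2, SAP 2.2) includes eyes in which implantation was abandoned after lens contact. The all-implanted analysis set requires successful implantation.

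**The concern.** For a first eye that was touched but not implanted, a site cannot follow both the table and the note. That eye belongs to the safety analysis set under either reading. Under the table it has scheduled postoperative examinations; under the note the subject leaves before them. Sites that read the section differently would follow exposed eyes differently. The serious adverse events that Protocol 11.1 defines by persistence to the end of the study would also have no scheduled exit examination for an eye handled under the note. Protocol Section 14 prohibits waivers, so whichever text a site follows, it departs from the other.

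**Working it through.** **Table against note, eye not implanted**

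| Eye | Lens contact | Table 8-1 | Note and second-eye paragraph | Result |
|---|---|---|---|---|
| First | No | Discontinue | Discontinue | Agree |
| First | Yes | Continue, safety only | Discontinue | Conflict |
| Second (first implanted) | No | Discontinue | Remain | Conflict |
| Second (first implanted) | Yes | Continue, no effectiveness assessments | Remain, all testing except binocular acuity and subject questionnaires | Status agrees |

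Two of the four cases conflict on status. In the last row the assessments differ, but the difference disappears if the table is read per eye.

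**Does other text settle it?**

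- Protocol Section 8 discontinues subjects excluded before first-eye surgery without lens contact, then refers to 8.4. It is silent on a touched first eye.
- Protocol 10.4.3 says that subjects whose lens is explanted "will continue in the study through Visit 3A and be followed for safety". It does not cover a lens that was never implanted.
- The text above Table 8-1 sends exclusions during surgery, and repeated failed implantation attempts, to the table without limiting it to one eye.
- The analysis-set definitions say which eyes count, not whether the subject stays.

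**Linked gap in visit timing.** If row 2 is followed for a touched first eye and no second-eye study surgery takes place, Visits 2A and 3A have no reference date. Only Visit 1 (Days 1-2 after first-eye surgery) is defined.

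**Size**

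Inputs: 168 randomized subjects, 84 per group (Protocol Section 8), hence at most 168 first eyes. The rate of touched but unimplanted first eyes is not given; 0.5% to 2% is an assumption.

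- Expected eyes: 168 × 0.005 = 0.84; 168 × 0.02 = 3.36.
- Chance of at least one: 1 − 0.995^168 = 0.569; 1 − 0.98^168 = 0.966.
- Scheduled examinations of a first eye after surgery (Table 3-1): slit lamp at Visits 1, 2A and 3A (3), intraocular pressure at the same visits (3), dilated fundus at Visits 2A and 3A (2). Total 3 + 3 + 2 = 8.
- Of these, the examinations dated without a second-eye operation are those at Visit 1: one slit lamp and one pressure reading, 2 in all.
- One eye as a share of the first eyes planned per group: 1/84 = 1.2%.

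**The case against.** The best defence of the text is that the note serves a different purpose: it exists to prevent implantation in one eye only, whereas row 2 concerns safety follow-up of an eye that has no study lens. That explains the note, but its instruction to discontinue from the study still clashes with row 2. Nor does the table say that row 2 is meant for second eyes only.

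On the untouched second eye, the paragraph under the note describes that exact situation, and Section 8 ties discontinuation without lens contact to the time before first-eye surgery. Reading specific text over general text is ordinary practice. This objection has force, and the case is therefore secondary. Still, no sentence gives the paragraph precedence over the table.

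On weight, there are no safety objectives or hypotheses, and safety information does not stop at discontinuation. Surgical problems and device deficiencies are recorded at surgery, investigators must assess each subject who leaves early (Protocol 10.4.2), and information received on adverse events unresolved at exit is documented up to database lock (Protocol 11.8). All of this stands: what is lost is scheduled examinations, not all safety data.

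It is also fair that the 0.5% to 2% rate has no support in the documents, and that the count of 8 includes visits whose dates depend on second-eye surgery. Both figures are therefore conditional. The Manual of Procedures was not available and may guide sites in practice, but it cannot remove a contradiction in the protocol.

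**Conclusion.** The concern holds. Protocol 8.4 contradicts itself for a first eye touched but not implanted, and no other section resolves it. The untouched second eye is a lesser conflict that a careful reader would probably settle from the more specific paragraph.

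The effect is small: about 1 to 3 first eyes, with a 57% to 97% chance of at least one, both resting on the assumed rate. The loss per eye under the note is between 2 and 8 scheduled examinations, depending on whether Visits 2A and 3A can be dated. The safety analyses are descriptive. The primary analysis is essentially unaffected, because an eye without a study lens is outside the all-implanted set under either rule. The text should be corrected because follow-up of exposed eyes should not depend on which sentence a site reads.

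**What to change.** Reconcile Table 8-1, the note and the second-eye paragraph so that each combination of first or second eye, touched or not, implanted or not, has one stated status consistent with the safety analysis set definition. State whether the table applies per eye or per subject. Add a sentence to Protocol 7.1 on how Visits 2A and 3A are timed when no second-eye study surgery takes place. The sponsor's clinical team decides the rule for each combination; this review does not propose one.

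The cost is an amendment to one table, its note, one paragraph and one timing sentence, with matching updates to the Manual of Procedures and site training. Protocol Section 4 requires ethics approval before implementation unless the change is only logistical or administrative or is needed to mitigate an immediate safety risk. Whether any visit is added or re-dated depends on the rule chosen.
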